10.1. Appendix 1: Regulatory, Ethical, and Study Oversight Considerations

10.1.1. Regulatory and Ethical Considerations

- This study will be conducted in accordance with the protocol and with the following:
 - consensus ethical principles derived from international guidelines, including the Declaration of Helsinki and Council for International Organizations of Medical Sciences (CIOMS) International Ethical Guidelines
 - applicable ICH GCP Guidelines, and
 - applicable laws and regulations.
 - The protocol, protocol amendments, ICF, Investigator Brochure, and other relevant documents (for example, advertisements) must be submitted to an IRB/IEC by the investigator and reviewed and approved by the IRB/IEC before the study is initiated.
 - Any amendments to the protocol will require IRB/IEC approval before implementation of changes made to the study design, except for changes necessary to eliminate an immediate hazard to study participants.
 - The investigator will be responsible for the following:
 - providing written summaries of the status of the study to the IRB/IEC annually or more frequently in accordance with the requirements, policies, and procedures established by the IRB/IEC
 - notifying the IRB/IEC of SAEs or other significant safety findings as required by IRB/IEC procedures
 - providing oversight of study conduct for participants under their responsibility and adherence to requirements of 21 CFR, ICH guidelines, the IRB/IEC, European regulation 536/2014 for clinical studies (if applicable), and all other applicable local regulations, and
 - reporting to the sponsor or designee significant issues related to participant safety, participant rights, or data integrity.
 - Investigator sites are compensated for participation in the study as detailed in the clinical trial agreement.

10.1.2. Financial Disclosure

Investigators and sub-investigators will provide the Sponsor with sufficient, accurate financial information as requested to allow the Sponsor to submit complete and accurate financial certification or disclosure statements to the appropriate regulatory authorities. Investigators are responsible for providing information on financial interests during the course of the study and for 1 year after completion of the study.

10.1.3. Informed Consent Process

- The investigator or his or her representative will explain a description of the investigational drug, the nature of the study, including the risks and benefits, to the participant or his or her legally authorized representative and answer all questions regarding the study.
- Participants must be informed that their participation is voluntary. Participants or their legally authorized representative will be required to sign a statement of informed consent that meets the requirements of 21 CFR 50, local regulations, ICH guidelines, Health Insurance Portability and Accountability Act (HIPAA) requirements, where applicable, and the IRB/IEC or study center.
- The medical record must include a statement that written informed consent was obtained before the participant was entered in the study and the date the written consent was obtained. The authorized person obtaining the informed consent must also sign the ICF.
- Participants must be re-consented to the most current version of the ICF(s) during their participation in the study
- A copy of the ICF(s) must be provided to the participant or the participant's legally authorized representative and is kept on file. Participants who are rescreened are required to sign a new ICF.

10.1.4. Data Protection

- Participants will be assigned a unique identifier by the sponsor to protect the participant's personal data. Any participant information, such as records, datasets, or tissue samples that are transferred to the sponsor, will contain the identifier only. Participant names or any information which would make the participant identifiable will not be transferred.
- The participant must be informed that the participant's personal study-related data will be used by the sponsor in accordance with local data protection law. The level of disclosure must also be explained to the participant who will be required to give consent for their data to be used as described in the informed consent. This is done by the site personnel through the informed consent process.
- The participant must be informed through the informed consent by the site personnel that their medical records may be examined by Clinical Quality Assurance auditors or other authorized personnel appointed by the sponsor, by appropriate IRB/IEC members, and by inspectors from regulatory authorities.
- The sponsor has processes in place to ensure information security, data integrity, and data protection. These processes address management of data transfer, and prevention and management of unauthorized access, disclosure, dissemination, alteration or loss of information or personal data. These processes include appropriate contingency plan(s) for appropriate and timely response in the event of a data security breach.

• The transfer of personal data is subject to appropriate safeguards through contractual agreements and processes. The sponsor's processes are compliant with local privacy laws and relevant legislations including the General Data Protection Regulation (GDPR).

10.1.5. Dissemination of Clinical Study Data

Reports

The sponsor will disclose a summary of study information, including tabular study results, on publicly available websites where required by local law or regulation.

The summary of results will be posted within the time frame specified by local law or regulation. If the study remains ongoing in some countries and a statistical analysis of an incomplete dataset would result in analyses lacking scientific rigor (for example, underpowered) or compromise the integrity of the overall analyses (for example, trial not yet unblinded), the summary of results will be submitted within 1 year after the end of the study globally or as soon as available, whichever is earlier.

Data

The sponsor provides access to all individual participant data collected during the trial, after anonymization, with the exception of pharmacokinetic or genetic data.

Data are available to request 6 months after the indication studied has been approved in the US and EU and after primary publication acceptance, whichever is later. No expiration date of data requests is currently set once data are made available.

Access is provided after a proposal has been approved by an independent review committee identified for this purpose and after receipt of a signed data-sharing agreement.

Data and documents, including the study protocol, statistical analysis plan, clinical study report, and blank or annotated case report forms, will be provided in a secure data-sharing environment for up to 2 years per proposal.

For details on submitting a request, see the instructions provided at www.vivli.org.

10.1.6. Data Quality Assurance

- All participant data relating to the study will be recorded on printed or electronic CRF unless transmitted to the Sponsor or designee electronically (for example, laboratory data). The investigator is responsible for verifying that data entries are accurate and correct by physically or electronically signing the CRF.
- The investigator must maintain accurate documentation (source data) that supports the information entered in the CRF.
- The investigator must permit study-related monitoring, audits, IRB/IEC review, and regulatory agency inspections and provide direct access to source data documents.

- Monitoring details describing strategy (for example, risk-based initiatives in operations and quality, such as risk management and mitigation strategies and analytical risk-based monitoring), methods, responsibilities and requirements, including handling of noncompliance issues and monitoring techniques are provided in the Monitoring Plan.
- The Sponsor or designee is responsible for the data management of this study, including quality checking of the data.
- The Sponsor assumes accountability for actions delegated to other individuals (for example, contract research organizations).
- Study monitors will perform ongoing source data verification to confirm that data entered into the CRF by authorized site personnel are accurate, complete, and verifiable from source documents; that the safety and rights of participants are being protected; and that the study is being conducted in accordance with the currently approved protocol and any other study agreements, ICH GCP, and all applicable regulatory requirements.
- Records and documents, including signed ICFs, pertaining to the conduct of this study must be retained by the investigator for the time period outlined in the Clinical Trial Agreement unless local regulations or institutional policies require a longer retention period. No records may be destroyed during the retention period without the written approval of the Sponsor. No records may be transferred to another location or party without written notification to the Sponsor.
- In addition, Sponsor or its representatives will periodically check a sample of the participant data recorded against source documents at the study site. The study may be audited by Sponsor or its representatives, and/or regulatory agencies at any time. Investigators will be given notice before an audit occurs.

Data Capture System

The investigator is responsible for ensuring the accuracy, completeness, legibility, and timeliness of the data reported to the Sponsor.

An EDC will be used in this study for the collection of CRF data. The investigator maintains a separate source for the data entered by the investigator or designee into the Sponsor-provided EDC system. The investigator is responsible for the identification of any data to be considered source and for the confirmation that data reported are accurate and complete by signing the CRF.

Additionally, eCOA data (questionnaires and scales) will be directly recorded by the patient, into an instrument (for example, an electronic device). The eCOA data will serve as the source documentation, and the investigator does not maintain a separate, written, or electronic record of these data.

Data collected via the Sponsor-provided data capture system(s) will be stored at third party (at third parties). The investigator will have continuous access to the data during the study and until decommissioning of the data capture system(s). Prior to decommissioning, the investigator will receive an archival copy of pertinent data for retention.

Data managed by a central vendor, such as laboratory test data, will be stored electronically in the central vendor's database system and will be provided to the investigator for review and retention. Data will subsequently be transferred from the central vendor to the Sponsor data warehouse.

Data from complaint forms submitted to Sponsor will be encoded and stored in the global product complaint management system.

10.1.7. Source Documents

- Source documents provide evidence for the existence of the participant and substantiate the integrity of the data collected. Source documents are filed at the investigator's site.
- Data reported on the CRF or entered in the eCRF that are transcribed from source documents must be consistent with the source documents or the discrepancies must be explained. The investigator may need to request previous medical records or transfer records, depending on the study. Also, current medical records must be available.

10.1.8. Study Closure

Study site participation may be discontinued if the Sponsor or its designee, the investigator, or the ERB of the study site judges it necessary for medical, safety, regulatory, or other reasons consistent with applicable laws, regulations, and GCP.

10.2. Appendix 2: Protocol JZLC ECOG Performance Status

Activity Status	Description
0	Fully active, able to carry on all pre-disease performance without restriction
1	Restricted in physically strenuous activity but ambulatory and able to carry out work of a light or sedentary nature, for example, light housework and office work
2	Ambulatory and capable of all selfcare but unable to carry out any work activities. Up and about more than 50% of waking hours
3	Capable of only limited selfcare, confined to bed or chair more than 50% of waking hours
4	Completely disabled. Cannot carry on any selfcare. Totally confined to bed or chair
5	Dead.

ECOG Performance Status

Source: Oken et al. 1982.

10.3. Appendix 3: Protocol JZLC RECIST Criteria 1.1

Response and progression will be evaluated in this study using the international criteria proposed by the New Response Evaluation Criteria in Solid Tumors (RECIST): Revised RECIST Guideline (version 1.1; Eisenhauer et al. 2009).

Measurability of Tumor at Baseline

Tumor lesions/lymph nodes will be categorized at baseline as measurable or nonmeasurable. Measurable disease is defined by the presence of at least 1 measurable lesion.

Measurable

Tumor lesions: measured in at least 1 dimension (longest diameter in the plane of measurement is to be recorded) with a minimum size of

- 10 mm by CT or MRI scan (slice thickness \leq 5 mm)
- 10 mm caliper measurement by clinical exam (non-measurable lesions if cannot be accurately measured with calipers), and
- 20 mm by chest X-ray.

Malignant lymph nodes: to be considered pathologically enlarged and measurable, a lymph node must be ≥ 15 mm in short axis when assessed by CT scan (CT scan thickness recommended to be ≤ 5 mm).

Nonmeasurable

All other lesions, including small lesions (longest diameter <10 mm or pathological lymph nodes with \geq 10 to <15 mm short axis) as well as truly nonmeasurable lesions. Lesions considered truly non-measurable include: leptomeningeal disease, ascites, pleural/pericardial effusions, lymphangitis cutis/pulmonis, inflammatory breast disease, lymphangitis involvement of skin or lung, abdominal masses/abdominal organomegaly identified by physical exam that is not measurable by reproducible imaging techniques.

Special Considerations for Lesion Measurability

Bone lesions:

- Bone scan, PET scan, or plain films are not considered adequate imaging techniques to measure bone lesions.
- Lytic bone lesions or mixed lytic-blastic lesions, with identifiable soft tissue components, that can be evaluated by cross sectional imaging techniques, such as CT or MRI, can be considered measurable lesions if the soft tissue component meets the definition of measurability.
- Blastic bone lesions are non-measurable.

Cystic lesions:

• Simple cysts should not be considered as malignant lesions (neither measurable nor nonmeasurable).

• Cystic lesions thought to represent cystic metastases can be considered as measurable lesions if they meet the definition of measurability. If noncystic lesions are presented in the same patients, these are preferred for selection as target lesions.

Lesions with Prior Local Treatment:

• Tumor lesions situated at a previously irradiated area, or in an area subjected to other loco-regional therapy, are non-measurable unless there has been demonstrated progression in the lesion.

Baseline Documentation of Target and Non-Target Lesion

Target Lesions

When more than 1 measurable lesion is present at baseline, all lesions up to a maximum of 5 lesions total (and a maximum of 2 lesions per organ) representative of all involved organs should be identified as target lesions and will be recorded and measured at baseline. Non-nodal target lesions should be selected on the basis of their size (lesions with the longest diameter), be representative of all involved organs, and can be reproduced in repeated measurements. Measurable lymph nodes are target lesions if they meet the criteria of a short axis of <15 mm by CT scan. All measurements are to be recorded in the CRF in millimeters (or decimal fractions of centimeters [cm]).

Nontarget Lesions

All other lesions (or sites of disease) are identified as nontarget lesions (chosen based on their representativeness of involved organs and the ability to be reproduced in repeated measurements) and should be recorded at baseline. Measurement of these lesions are not required but should be followed as "present," "absent," or in rare cases "unequivocal progression." In addition, it is possible to record multiple nontarget lesions involving the same organ as a single item on the CRF (for example, multiple liver metastases recorded as 1 liver lesion).

Lymph nodes with short axis ≥ 10 mm but < 15 mm should be considered nontarget lesions. Nodes that have a short axis < 10 mm are considered nonpathological and are not recorded or followed.

Specifications by Methods of Measurement

All measurements should be recorded in metric notation, using a ruler or calipers if clinically assessed. All baseline evaluations should be performed as closely as possible to the beginning of treatment and never more than 4 weeks before the beginning of the treatment (except for the baseline bone scintigraphy, which may be obtained up to 45 days prior to the beginning of the treatment).

The same method of assessment and the same technique should be used to characterize each identified and reported lesion at baseline and during follow-up. Imaging-based evaluation is should always be done rather than clinical examination unless the lesion(s) being followed cannot be imaged but are assessed by clinical exam.

An adequate volume of a suitable contrast agent should be given so that the metastases are demonstrated to best effect and a consistent method is used on subsequent examinations for any given patient. If prior to enrollment it is known a patient is not able to undergo CT scans with IV contrast due to allergy or renal insufficiency, the decision as to whether a non-contrast CT or MRI (with or without IV contrast) should be used to evaluate the patient at baseline and follow-up should be guided by the tumor type under investigation and the anatomic location of the disease.

Clinical Lesions: clinical lesions will only be considered measurable when they are superficial and ≥ 10 mm diameter as assessed using calipers (for example, skin nodules). For the case of skin lesions, documentation by color photography, including a ruler to estimate the size of the lesion, is recommended. When lesions can be evaluated by both clinical exam and imaging, imaging evaluation should be undertaken since it is more objective and may be reviewed at the end of the study.

Chest X-ray: chest CT is preferred over chest X-ray when progression is an important endpoint. Lesions on chest X-ray may be considered measurable if they are clearly defined and surrounded by aerated lung.

CT and MRI: CT scan is the best currently available and reproducible method to measure lesions selected for response assessment. Measurability of lesions on CT scan is based on the assumption that CT slice thickness is \leq 5 mm. When CT scan has slice thickness >5 mm, the minimum size for a measurable lesion should be twice the slice thickness. MRI is also acceptable in certain situations (for example, for body scans). If there is concern about radiation exposure at CT, MRI may be used instead of CT in selected instances.

Ultrasound: ultrasound should not be used to measure lesion size. Ultrasound examinations cannot be reproduced in their entirety for independent review at a later date, and because they are operator dependent, it cannot be guaranteed that the same technique and measurements will be taken from 1 assessment to the next. If new lesions are identified by ultrasound in the course of the study, confirmation by CT or MRI is advised.

Endoscopy, Laparoscopy: the utilization of these techniques for objective tumor evaluation is not advised. However, such techniques can be useful to confirm complete pathological response when biopsies are obtained or to determine relapse in trials where recurrence following CR or surgical resection is an endpoint.

Tumor Markers: tumor markers alone cannot be used to assess tumor response. If markers are initially above the upper normal limit, they must normalize for a patient to be considered in CR. Specific guidelines for both prostate-specific antigen response (in recurrent prostate cancer) and CA-125 response (in recurrent ovarian cancer) have been published.

Cytology, Histology: these techniques can be used to differentiate between PRs and CR in rare cases if required by protocol (for example, residual lesions in tumor types, such as germ cell tumors, where known residual benign tumors can remain). When effusions are known to be a potential adverse effect of treatment (for example, with certain taxane compounds or

angiogenesis inhibitors), the cytological confirmation of the neoplastic origin of any effusion that appears or worsens during treatment can be considered if the measurable tumor has met criteria for response or SD in order to differentiate between response (or SD) and PD.

Pet Scan (FDG-PET, PET CT): PET is not recommended for lesion assessment. If a new lesion is found by PET, another assessment must be done by CT, unless the PET CT is of diagnostic quality. If CT is done to confirm the results of the earlier PET scan, the date of progression must be reported as the earlier date of the PET scan.

Bone Scan: If lesions measured by bone scan are reported at baseline, it is necessary to repeat the bone scan when trying to identify a CR or PR in target disease or when progression in bone is suspected.

Response Criteria

Evaluation of Target Lesions

Complete Response (CR): disappearance of all target lesions. Any pathological lymph nodes (whether target or non-target) must have reduction in short axis to <10 mm. Tumor marker results must have normalized.

Partial Response (PR): at least a 30% decrease in the sum of diameter of target lesions, taking as reference the baseline sum diameters.

Progressive Disease (PD): at least a 20% increase in the sum of the diameters of target lesions, taking as reference the smallest sum on study (including the baseline sum if that is the smallest). In addition to the relative increase of 20%, the sum must also demonstrate an absolute increase of at least 5 mm. The appearance of 1 or more new lesions is also considered progression.

For equivocal findings of progression (for example, very small and uncertain new lesions; cystic changes or necrosis in existing lesions), treatment may continue until the next scheduled assessment. If at the next scheduled assessment, progression is confirmed, the date of progression should be the earlier date when progression was suspected.

Stable Disease (SD): neither sufficient shrinkage to qualify for PR nor sufficient increase to qualify for PD, taking as reference the smallest sum diameters while on study.

Not Evaluable: when an incomplete radiologic assessment of target lesions is performed or there is a change in the method of measurement from baseline that impacts the ability to make a reliable evaluation of response.

Evaluation of Nontarget Lesions

Complete Response: disappearance of all nontarget lesions and normalization of tumor marker level. All lymph nodes must be non-pathological or normal in size (<10 mm short axis).

Non-CR/ non-PD: persistence of 1 or more nontarget lesions and/or maintenance of tumor marker level above the normal limits.

Progressive Disease: unequivocal progression of existing nontarget lesions. The appearance of 1 or more new lesions is also considered progression.

Not Evaluable: when a change in method of measurement from baseline occurs and impacts the ability to make a reliable evaluation of response.

Evaluation of Best Overall Response

The best overall response is the best response recorded from the start of the study treatment until the earliest of objective progression or start of new anticancer therapy, taking into account any requirement for confirmation. The patient's best overall response assignment will depend on the findings of both target and nontarget disease and will also take into consideration the appearance of new lesions. The Best Overall Response will be calculated via an algorithm using the assessment responses provided by the investigator over the course of the trial.

Time Point Response

It is assumed that at each protocol-specified time point, a response assessment occurs (when no imaging/measurement is done at all at a particular time point, the patient is not evaluable (NE) at that time point). Table 1 provides a summary of the overall response status calculation at each time point for patients who have *measurable disease* at baseline.

Target Lesions	Non-Target Lesions	New Lesions	Overall Response
CR	CR	No	CR
CR	Non-CR/non-PD	No	PR
CR	Not evaluated	No	PR
PR	Non-PD or not all evaluated	No	PR
SD	Non-PD or not all evaluated	No	SD
Not all evaluated	Non-PD	No	NE
PD	Any	Yes or No	PD
Any	PD	Yes or No	PD
Any	Any	Yes	PD

Table 2: Time Point Response: Patients with Target (± Nontarget) Disease

Abbreviations: CR = complete response; NE = not evaluable; PD = progressive disease; PR = partial response; SD = stable disease.

Table 3 is to be used when patients have *nonmeasurable* disease only.

Nontarget Lesions	New Lesions	Overall Response	
CR	No	CR	
Non-CR/non-PD	No	Non-CR/non-PD ^a	
Not all evaluated	No	NE	
Unequivocal PD	Yes or No	PD	
Any	Yes	PD	

Table 3: Time Point Response: Patients with Nontarget Disease Only

Abbreviations: CR = complete response; NE = not evaluable; PD = progressive disease.

^a non-CR/non-PD is preferred over SD for nontarget disease.

Frequency of Tumor Reevaluation

A baseline tumor evaluation must be performed within 4 weeks before patient begins study treatment. Frequency of tumor reevaluation while on and adapted to treatment should be protocol specific and adapted to the type and schedule of treatment. In the context of Phase 2 studies where the beneficial effect therapy is not known, follow-up every 6-8 weeks is reasonable. Normally, all target and non-target sites are evaluated at each assessment using the same method. However, bone scans may need to be repeated only when CR is identified in target disease or when progression in bone is suspected.

Confirmatory Measurement/Duration of Response

Confirmation

The main goal of confirmation of objective response in clinical trials is to avoid overestimating the response rate observed. The confirmation of response is particularly important in *nonrandomized trials* where response (CR/PR) is the primary end point. In this setting, to be assigned a status of PR/CR, changes in tumor measurements must be confirmed by repeat assessments that should be performed no less than 4 weeks after the criteria for response are first met. To confirm a response of CR, a full assessment of all target and nontarget lesions that were present at baseline must occur, including those measured by bone scan. To confirm a PR or SD, a full assessment of target lesions that were present at baseline must occur; assessment of nontargets is not required.

However, in *randomized trial* (Phase 2 or 3) or studies where SD or progression is the primary endpoints, confirmation of response is not required. But elimination of the requirement may increase the importance of central review to protect against bias, in particular for studies which are not blinded.

In the case of SD, follow-up measurements must have met the SD criteria at least once after start of treatment at a minimum interval not less than 6 weeks measured from randomization.

Duration of Overall Response

The duration of overall response is measured from the time measurement criteria are first met for CR or PR (whichever is first recorded) until the first date that disease is recurrent or objective progression is observed (taking as reference for PD the smallest measurements recorded on study).

The duration of overall CR is measured from the time measurement criteria are first met for CR until the first date that recurrent disease is objectively documented.

Duration of Stable Disease

Stable disease is measured from the start of the treatment (in randomized trials, from date of randomization) until the criteria for objective progression are met, taking as reference the smallest sum on study (if the baseline sum is the smallest, that is the reference for calculation of PD).

Independent Review of Response and Progression

When objective response (CR + PR) is the primary end point, and when key drug development decisions are based on the observation of a minimum number of responders, it is recommended that all claimed responses be reviewed by an expert(s) independent of the study. If the study is a randomized trial, ideally reviewers should be blinded to treatment assignment.

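### The target-lesion sentence for lymph nodes in Appendix 3 uses <15 mm, which contradicts the appendix's own ≥15 mm measurability rule and its nontarget rule

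*Protocol*

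**What the plan says.** Four statements in Protocol Appendix 3 (Section 10.3) classify lymph nodes by short axis.

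- **Measurable:** "to be considered pathologically enlarged and measurable, a lymph node must be ≥ 15 mm in short axis". The Nonmeasurable paragraph that follows lists pathological nodes of 10 to <15 mm.
- **Target Lesions:** "Measurable lymph nodes are target lesions if they meet the criteria of a short axis of <15 mm by CT scan".
- **Nontarget Lesions:** "Lymph nodes with short axis ≥ 10 mm but < 15 mm should be considered nontarget lesions".
- **Nontarget Lesions, next sentence:** "Nodes that have a short axis < 10 mm are considered nonpathological and are not recorded or followed".

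The appendix then applies different progression tests. For target lesions the test is "at least a 20% increase in the sum of the diameters of target lesions", measured from the smallest sum on study, and "the sum must also demonstrate an absolute increase of at least 5 mm". For nontarget lesions it is "unequivocal progression of existing nontarget lesions", with no measured threshold. New lesions count as progression in either case.

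Protocol Section 8.1.3 makes RECIST v1.1, cited together with Appendix 3, the primary standard for response and for the date of progression. SAP Section 4.8.1 treats every patient with at least one lesion on the baseline target form as having measurable disease. SAP Section 3 defines the ORR-evaluable population by measurable disease at baseline. The SAP gives no nodal threshold of its own.

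**The concern.** The sign in the target-lesion sentence is the reverse of the one in the measurability rule. This is current operational text telling sites which lesions to record and measure at baseline. It is neither background nor part of an amendment log.

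Two things depend on the classification. The first is the progression test: a target node contributes millimetres to a sum with fixed thresholds, whereas a nontarget node is judged qualitatively. Investigator-assessed PFS is the endpoint for all three primary hypotheses, and the target sum is one route to a PFS event, beside nontarget progression, new lesions and death. The second is ORR-evaluable membership, because the SAP infers measurable disease from the target form and does not check lesion size.

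**Working it through.** The plan states no figure that depends on this sentence, so there is nothing to reproduce. The check compares the size classes and then works through the progression rule.

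**Step 1. Size classes (short axis, CT), all from Appendix 3**

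| Node | Measurability rule | Nontarget paragraph | Target sentence, literal | Target sentence, <15 mm as the working cut |
|---|---|---|---|---|
| <10 mm | not measurable | not recorded | not selected | not recorded, so no practical effect |
| 10 to <15 mm | nonmeasurable | nontarget | not selected (not measurable) | target, in conflict with nontarget |
| ≥15 mm | measurable | not addressed by size | not selected (not <15 mm) | not selected |

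- *Literal reading.* The sentence requires a node to be measurable (≥15 mm) and also <15 mm. No size meets both, so the sentence selects no node.
- *Cut-only reading.* If the reader passes over the word measurable, the recorded nodes selected are those of 10 to <15 mm, exactly the set that the nontarget rule claims.
- *With ≥15 mm in the sentence.* The classes become <10 mm not recorded, 10 to <15 mm nontarget, and ≥15 mm measurable and eligible as target. There is no overlap and no gap.

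**Step 2. Can the classification change a progression call?** Lesion sizes here are assumed for illustration; none comes from the documents. Target progression needs (increase ÷ smallest sum) ≥ 0.20 and an increase ≥ 5 mm.

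- *Extreme case, one 12 mm node as the only target, growing to 17 mm:* the increase is 17 − 12 = 5 mm, and 5 ÷ 12 = 41.7%. Both thresholds are met. As a nontarget node, the same growth is progression only if judged unequivocal.
- *When is 5 mm enough?* 5 ÷ S ≥ 0.20 requires S ≤ 25 mm.
- *The same node beside a stable 30 mm target:* the sum is 12 + 30 = 42 mm, and 5 ÷ 42 = 11.9%, which is not progression.
- *Effect in the other direction:* for the 30 mm lesion alone, progression needs 0.20 × 30 = 6 mm. With a stable 12 mm node wrongly in the sum it needs 0.20 × 42 = 8.4 mm, so progression would be called later.

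Misclassification can therefore bring a progression call forward or delay it, depending on the other targets.

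**Step 3. ORR-evaluable membership.** Under SAP Section 4.8.1, a 10 to <15 mm node entered on the target form makes the patient count as having measurable disease. Conversely, a patient whose only measurable lesion is a node of ≥15 mm would not be counted if the site followed the printed sentence and left the target form empty. Either error needs a patient with no other target lesion.

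**The case against.** The strongest reply is that the sentence is a visible slip with little effect. Its subject is measurable nodes, and the appendix has just defined those as ≥15 mm, so an instruction that no node can meet sends the reader back to that definition. The same paragraph opens with a general rule making measurable lesions targets, up to five in total and two per organ, so a 20 mm node can still qualify. Sites also have the cited RECIST 1.1 guideline and a Site Imaging Manual. All of this stands as a reason to expect a small effect, but none of it makes the sentence consistent with the rest of the appendix.

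A reader might infer more than the documents support:

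- *That nontarget nodes will enter the target sum and drive PFS.* This follows only on the cut-only reading, and the target sum is just one route to an event.
- *That the 12 to 17 mm example is typical.* It is an extreme case. A patient whose only lesion is a 12 mm node has no measurable disease under the appendix and would not meet inclusion criterion 8 on that lesion.
- *That criterion 8 itself is compromised.* Eligibility rests on measurability, which the appendix defines consistently; the disputed sentence governs target selection.
- *That disagreement with the blinded independent review will widen.* The BIRC analysis also uses RECIST 1.1, and nothing shows either reader applying <15 mm.
- *That one arm is favoured.* The sentence applies to all arms alike, and no differential effect is shown.

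A text-extraction fault in the sign is possible. The neighbouring nodal thresholds read coherently, which makes it unlikely.

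**Conclusion.** The inconsistency is real on either reading and should be corrected. It is a wrong decision threshold in the appendix that Section 8.1.3 cites for dating progression, and the SAP does not resolve it. Most plausibly it is a reversed inequality sign.

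The consequence is conditional. Only if sites applied the printed cut would some progression calls or dates, and some ORR-evaluable classifications, change. The documents give neither the share of participants with nodal disease nor any sign that a site used the <15 mm cut, so the size is unknown and probably small. No sample size, power, alpha or event count depends on it. The conclusion assumes that the printed sign is confirmed in the source PDF.

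**What to change.** 1. Check the sign against the source PDF.
2. If it is confirmed, change <15 mm to ≥15 mm in the target-lesion sentence, so that it agrees with the measurability and nontarget rules of the same appendix.
3. Confirm that the Site Imaging Manual uses the same cut.
4. Query every baseline target node recorded with a short axis below 15 mm. This shows directly whether any site applied the printed rule. The reverse error, a node of ≥15 mm left off the target list, is harder to see because the appendix does not require nontarget lesions to be measured.
5. State how any affected participants will be handled before the final PFS results are seen.

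The wording change is one symbol, but it is not free: Section 10.1.1 requires IRB/IEC approval of an amendment before changes to the study design are implemented. SAP Version 5 was approved after both futility interims, so many baseline target selections had already been made, and correcting the text alone does not deal with them. The query in step 4 does, at the cost of one data listing and its follow-up.
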